Mechanistic (exploratory) aims: To obtain preliminary estimates of the effects of the POSTHOC app vs. usual care on patient-reported symptoms including neuropathy (CIPN20), pain (Brief Pain Inventory), cognitive impairment (FACT-Cog), fatigue (Brief Fatigue Inventory), and anxiety and depression (Hospital Anxiety and Depression Scale and Distress Thermometer), as well as clinician-reported patient health (e.g., ECOG performance status), and healthcare utilization (e.g., number of unplanned medical encounters). In addition to questionnaires, we will also assess how key symptoms are affected using ecological momentary assessment.

1 To assess cross-sectional associations between health behaviors (physical activity, diet, sleep) and cumulative symptom burden at baseline.

2 To explore associations between changes in health behaviors (physical activity, diet, sleep) and cumulative symptom burden from baseline to 6 weeks and baseline to 12 weeks.

3 To explore associations between adherence to the intervention and changes in the same measures.

2 * Discuss the research design including but not limited to such issues as: probability of group assignment, potential for subject to be randomized to placebo group, use of control subjects, etc.:

This is a phase I/II feasibility/preliminary efficacy randomized controlled trial. Participants will be randomized 2:1, intervention (n=36): usual care (n=18). There is a 67% chance of any given participant to be in the intervention group, and a 33% chance of any given participant to be in the usual care group.

Neither the study PI nor the coordinators will be blinded due to their active involvement in participant interaction and data collection. The participants cannot be blinded due to the nature of the intervention.

3 * Describe the relevant prior experience and gaps in current knowledge. Describe any relevant preliminary data:

After completion of cancer treatment, people are faced with many issues including symptoms that may or may not become chronic, many instructions as to what to do next (e.g., follow-up appointments, referrals), and uncertainty regarding the involvement of their oncology team in their health moving forward. Survivorship Care Plans were implemented to help solve these problems.

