Upon opening of the study, we expect that approximately 3-5 participants will be recruited per month for approximately 14 months. Data originating from questionnaires, activity trackers, the POSTHOC app, and exit interviews will be entered, processed, and cleaned (as applicable) as they come in. Data analysis will take place soon after all data are collected.

These data will be used to inform a follow-on randomized clinical trial, for example, a phase III or multisite clinical trial. These data will also inform design refinements to improve the POSTHOC app toward supporting the needs of target users. It is anticipated that at least two manuscripts will emerge from this study, the first of which will be submitted for publication within one year of the study closing (the primary aims paper).
5. * Describe any additional participant requirements:

None

Sample Size and Data Analysis

If you uploaded a separate research protocol document in the 'Research Protocol' page, cite the applicable section and page numbers from that document in the answer boxes below.

1 * Provide the rationale and sample size calculations for the proposed target population:

This is a two-arm randomized controlled trial that will assess the feasibility of recruitment and retention to a 12-week behavioral health intervention trial facilitated by the POSTHOC app as well as the preliminary efficacy of behavioral health intervention vs. a control arm on the treatment of cumulative symptom burden in people with cancer.

Under assumptions of ANCOVA and pre-post correlation of 0.65 (Born et al., 2007), a sample size of n=46 (after 15% missing data) provides 80% power to detect a standardized between-arm difference of 0.50, which corresponds to a medium-sized and clinically meaningful effect (Norman et al., 2003).

Implications for clinical significance:

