The cumulative symptom burden is a sum of the severity of 13 symptoms. It has a range of 0-130. Our power calculation is based on data from a single-arm pilot study that we conducted among a similar group of cancer survivors. In order to achieve a standardized between-arm difference of 0.50, which corresponds to a medium-sized and clinically meaningful effect, we assumed a pre-post correlation of 0.5 (typical for this type of patient-reported outcome). With 80% power, we calculated a minimal sample size of n=46 after an estimated 15% attrition. Effect size (ES) corresponds to how many standard deviations in cumulative symptom burden the groups differ by:

$$ES = (\Delta_{POSTHOC} - \Delta_{control}) / SD_{pooled}$$

$\Delta_{POSTHOC}$ = the difference in cumulative symptom burden from pre- to post-intervention in the POSTHOC group

$\Delta_{control}$ = the difference in cumulative symptom burden from pre- to post-intervention in the control group

SD_{pooled} = the standard deviation of cumulative symptom burden measures for all participants at baseline

From preliminary data generated from a previous study ([name] et al., 2022), we had a standard deviation of cumulative symptom burden from a similar symptom inventory of 17.04.

$$0.50 = (\Delta_{POSTHOC} - \Delta_{control}) / 17.04$$

$$\text{Therefore, } (\Delta_{POSTHOC} - \Delta_{control}) = 8.52$$

Thus, we expect that the cumulative symptom burden will decrease 8.5 points more in the POSTHOC group compared to the control group from baseline to 12 weeks.

2 * Provide the plan for data analysis. Include in the description the types of comparisons that are planned (e.g., comparison of means, comparison of proportions, regressions, analysis of variance, etc.), which is the primary comparison/analysis, and how the analyses proposed will relate to the primary purposes of the study:

Analysis plan for Aim 1. Assess the feasibility of the POSTHOC app by patients newly transitioning from active cancer treatment (n=36). We will calculate the percentage of patients who used the POSTHOC app at least 3 times per week. When we estimate feasibility, a 95% CI will span approximately $\pm 15\%$. For example, if we observe 27/36 (75%) participants used the app, the CI will be 58.9-86.2%.

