Analysis plan for Aim 2. Our data from Aim 2 will provide estimated effect sizes to inform the sample size of a confirmatory Phase III RCT, per clinical trial guidelines (Freidlin et al., 2012). Our planned sample size is 54 participants total (36 in the POSTHOC group, 18 in the control group); we factor in 15% missing data to yield evaluable data from 46 participants total (31 for POSTHOC, 15 for control). Hypotheses will be tested at $\alpha=0.15$ (2-tailed) as appropriate for Phase I/II studies of this size (Rubinstein et al., 2005).

Aim: Obtain a preliminary estimate of the effect of the POSTHOC app vs. usual care on cumulative patient-reported symptom burden from the MD Anderson Symptom Inventory (MDASI).

Analysis plan: Cumulative severity is the sum of the individual severity levels from the 13 core symptoms from the MD Anderson Symptom Inventory (ranging 0-130). We will use the analysis of covariance (ANCOVA) with cumulative severity at Week 6 as the outcome, study arm (POSTHOC app vs. usual care) as the main independent variable and cumulative symptom severity at Week 0 as a covariate. In case of significant imbalance in other factors between arms (e.g., age), we might include additional covariates in the model. We chose Week 6 as the primary time point because preliminary data from our group shows greater benefits of behavioral interventions at 6 vs. 12 weeks ([name] et al., in preparation). Similar ANCOVA models will evaluate the effects of the POSTHOC app vs. usual care for each outcome at Week 6 and Week 12. To evaluate the longitudinal trajectory of each outcome, we will use repeated measures linear mixed model (LMM) incorporating the specific outcome at all three time points and using a linear contrast to test effects of POSTHOC app vs. usual care. We will use the intent-to-treat principle.

Analyses for Aim 3 and the Exploratory Aims that evaluate symptoms and feelings are analogous to Aim 2, using ANCOVA and LMM to assess the effects of the POSTHOC app vs. usual care control on each outcome. Exploratory analyses will include tests of moderation effects on the POSTHOC app by physical activity adherence, sex, age, etc.

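### The stated 80% power for Aim 2 does not follow from the plan's inputs: with 31:15 evaluable and two-tailed alpha 0.15, power for 0.50 SD is about 73% (r = 0.65) or 65% (r = 0.50), and the plan uses both correlations for the same n

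*Combined protocol and SAP*

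**What the plan says.** Sample Size and Data Analysis, item 1, makes the power statement twice.

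- The opening statement begins "Under assumptions of ANCOVA and pre-post correlation of 0.65" and concludes that "a sample size of n=46 (after 15% missing data) provides 80% power to detect a standardized between-arm difference of 0.50".
- Under Implications for clinical significance, the plan keeps the 0.50 SD target but says "we assumed a pre-post correlation of 0.5 (typical for this type of patient-reported outcome". It then states: "With 80% power, we calculated a minimal sample size of n=46 after an estimated 15% attrition". For the conversion to points it reports that "we had a standard deviation of cumulative symptom burden from a similar symptom inventory of 17.04", which gives a difference of 8.52 points.

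The remaining inputs are elsewhere.

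- Justification, Objective, & Research Design, item 2: "Participants will be randomized 2:1, intervention (n=36): usual care (n=18".
- Sample Size and Data Analysis, item 2, Analysis plan for Aim 2: 15% missing data leaves "evaluable data from 46 participants total (31 for POSTHOC, 15 for control".
- The same plan for Aim 2: "Hypotheses will be tested at $\alpha=0.15$ (2-tailed) as appropriate for Phase I/II studies of this size". The model is ANCOVA of the Week 6 score with the Week 0 score as covariate.

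**The concern.** There are two faults, and the first needs no calculation. In ANCOVA the residual variance is proportional to 1 - r², which is 0.5775 at r = 0.65 and 0.75 at r = 0.50. The second is about 30% larger than the first (0.75 / 0.5775 = 1.30). The same sample size, effect and alpha therefore cannot give the same power under both correlations, and a reader cannot tell which one the design rests on.

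The second fault is that neither correlation gives 80% once the plan's own allocation, attrition and alpha are used.

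This power statement is the plan's answer to the request for a sample-size rationale, and the results are meant to inform a Phase III trial. If the trial finds no difference, readers will take the chance of having missed a half-SD effect to be 20%. On the plan's inputs it is 27% or 35%. Sample-size work for the next trial would also inherit the unresolved correlation.

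**Working it through.** **Inputs, all from the plan**

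- Evaluable: n1 = 31, n2 = 15 (total 46). As a check, 54 × 0.85 = 45.9.
- Effect: d = 0.50 baseline SD. With SD 17.04 this is 0.50 × 17.04 = 8.52 points, which reproduces the plan's figure.
- Alpha 0.15, two-tailed. This appears in the Aim 2 analysis plan, not beside the power statement, and it is the only alpha the plan gives.
- ANCOVA with one covariate, so residual df = 46 - 3 = 43.
- Pre-post correlation r = 0.65 or 0.50.

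**Formula**

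ncp = [d / sqrt(1 - r²)] × sqrt[n1 × n2 / (n1 + n2)]

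The sample-size factor is sqrt(31 × 15 / 46) = 3.179. Power comes from the noncentral t distribution with 43 df and a two-sided critical value of 1.466.

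| | r = 0.65 | r = 0.50 |
|---|---|---|
| sqrt(1 - r²) | 0.760 | 0.866 |
| d / sqrt(1 - r²) | 0.658 | 0.577 |
| ncp | 2.092 | 1.836 |
| **Power, noncentral t** | **73.5%** | **64.6%** |
| Power, normal approximation | 74.3% | 65.4% |
| Chance of missing 0.50 SD (noncentral t) | 26.5% | 35.4% |
| Difference detectable with 80% power | 0.552 SD = 9.4 points | 0.629 SD = 10.7 points |
| Evaluable n for 80% at exact 2:1 | 57 (38:19) | 72 (48:24) |
| Randomised n after 15% loss | 57 / 0.85 → 68 | 72 / 0.85 → 85 |

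At r = 0.65, a total of 56 split 37:19 also reaches 80% (80.8%), so 56 and 57 differ only in how the 2:1 split is rounded. To reach 80% at 31:15, r would have to be about 0.725, a value the plan does not use.

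**Can 80% be recovered by another reading?**

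Each row changes at least one stated input; power is by noncentral t.

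| Change | r = 0.65 | r = 0.50 |
|---|---|---|
| All 54 analysed (36:18), no missing data | 79.3% | 70.6% |
| Equal allocation, 23:23 | 77.8% | 69.0% |
| One-sided alpha 0.15, 31:15 | 85.1% | 78.5% |
| One-sided alpha 0.15, 23:23 | 88.1% | 81.8% |
| Two-sided alpha 0.10, 31:15 | 66.1% | 56.5% |
| Two-sided alpha 0.05, 31:15 | 53.4% | 43.4% |
| Change-score analysis, two-sided 0.15, 31:15 | 67.0% | 55.4% |

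Every value close to 80% or above it sets aside a stated feature: the 15% loss, the 2:1 allocation or the two-tailed test. The 79.3% for the full 36:18 at r = 0.65 suggests that attrition may not have been deducted. Other rows come almost as close, so the origin of the 80% cannot be settled from the documents.

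**The case against.** The strongest reply is that this is a feasibility and preliminary-efficacy trial. Aim 1 is app use. Aim 2 seeks an early effect estimate for planning a larger trial, and the plan sets no rule that a significant Aim 2 result decides whether Phase III goes ahead. An estimate and its confidence interval do not depend on the power quoted in advance. At r = 0.65 the gap is also modest: 9.4 detectable points instead of 8.5, using an SD borrowed from a similar inventory.

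Much of this stands. It is why no change to enrolment is called for, and why over-reading of a null result is a risk rather than a certainty. The true power also depends on a correlation that nobody yet knows, so 73% and 65% are conditional on the plan's two values.

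The reply does not rescue the figure. The plan states a directional hypothesis for Aim 2, sets an alpha for testing it and offers 80% power as the rationale for its size. The normal approximation does not close the gap either: it still falls about 6 points short at r = 0.65 and 15 at r = 0.50.

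**Conclusion.** The concern holds. The two correlations contradict each other, and the 80% is not supported under either. Power for 0.50 SD is 6.5 points below the stated value at r = 0.65 and 15.4 points below at r = 0.50. These results assume 46 evaluable participants split 31:15, ANCOVA on a single baseline covariate, equal residual variance in the arms, and the two-tailed alpha of 0.15 from the Aim 2 analysis plan. That attrition was not taken off is a possible explanation only, and the conclusion does not depend on it.

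**What to change.** Choose one pre-post correlation, give its source, and use it in both places in item 1. State alpha, its sidedness and the 31:15 split beside the power figure. Suggested wording:

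> With 46 evaluable participants (31 POSTHOC, 15 control) and a two-sided alpha of 0.15, ANCOVA adjusting for the baseline score has about 73% power to detect a difference of 0.50 SD if the pre-post correlation is 0.65 (about 65% if it is 0.50). The difference detectable with 80% power is 0.55 SD, or 9.4 points (0.63 SD, or 10.7 points, if the correlation is 0.50).

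If one correlation is adopted as the planning value, the other can stay as a labelled sensitivity case.

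The cost is a revision to the wording of the sample-size section. Enrolment, procedures, endpoint and analysis model are unchanged. The price is a less favourable power statement. If 80% for 0.50 SD were to be kept as a requirement, the trial would have to randomise 68 (r = 0.65) or 85 (r = 0.50) instead of 54, which its preliminary purpose does not demand.

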During the initial meeting with the patient, we will have a member of the study staff explain the purpose of the study and then, if the person is interested in joining the study, obtain their consent for participation. The initial meeting will occur in person, via telephone, or video conference, depending on participant preference. After consent all participants will receive a paper-based Survivorship Care Plan via MyPortfolio. We will administer questionnaires including an On Study form that includes demographics and clinical characteristics and baseline assessments (approximately 35-50 minutes). Questionnaires will be administered via REDCap unless the participant would prefer paper-based questionnaires through the mail. Questionnaires can be completed on any device that has internet, including their computer, tablet, or smartphone, and do not need to be completed in a single sitting; they can be completed on the participants' own time. Participants will receive a Fitbit smartwatch activity tracker and orientation to use of the tracker. Participants will wear the activity tracker for 7 days to assess physical activity and sleep. We will also conduct ecological momentary assessment (EMA) via the activity tracker and POSTHOC app for these 7 days during which participants will be prompted (via notification) to answer 5 questions per day—the default times will be 9am, 12:30pm, 4pm, and 7:30pm but can be adjusted based on the participant's schedule and preferences (ideally begin 1-2 hours after waking). These questions will capture key symptoms—distress, fatigue, pain, numbness/tingling, and interference of any symptoms with daily activity on a scale from 0-10. Dietary intake data will be collected via telephone or video conference by a study team member using the 24-hour (ASA24) Dietary Assessment Tool at baseline, week 6, and week 12.

During the baseline week, all participants will have a "light" version of the POSTHOC app that only has these initial data collection features (e.g., activity tracking, EMA data collection) during the baseline week.

After baseline data collection, participants will be randomized. Randomization will occur 2:1 for POSTHOC app (N=36) vs. control (N=18). We will use a computer-generated table with random blocks of 3 and 6. We will stratify by whether the participant had chemotherapy or not (yes/no).

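### Randomisation is stratified by chemotherapy, but the primary ANCOVA omits the stratum, and other covariates may enter under an undefined imbalance rule

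*Combined protocol and SAP*

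**What the plan says.** **Randomisation** (Study Procedures, item 1). Allocation is 2:1, 36 to the app and 18 to control: "We will use a computer-generated table with random blocks of 3 and 6". On strata: "We will stratify by whether the participant had chemotherapy or not (yes/no".

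**Primary model** (Sample Size and Data Analysis, item 2, Analysis plan for Aim 2). The outcome is cumulative severity at Week 6. The model has "study arm (POSTHOC app vs. usual care) as the main independent variable and cumulative symptom severity at Week 0 as a covariate". Similar ANCOVAs are planned for each outcome at Weeks 6 and 12. Tests are two-sided at 0.15, with 31 and 15 evaluable participants expected.

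**Mixed model** (same place). For trajectories, "we will use repeated measures linear mixed model (LMM) incorporating the specific outcome at all three time points and using a linear contrast". No covariates are listed, so the stratum is unspecified rather than expressly excluded.

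**Further covariates** (same place). "In case of significant imbalance in other factors between arms (e.g., age), we might include additional covariates in the model". Age is the only example. No test, threshold, list or time of decision is given.

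No other section puts chemotherapy into a model or defines the imbalance rule.

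**The concern.** Blocking within chemotherapy strata keeps the arms alike on chemotherapy, so the true sampling variance of the arm difference is smaller when chemotherapy is prognostic. A model without the stratum leaves the chemotherapy variation in its residual. Its reported standard error is then close to that of an unstratified trial. The interval is too wide and the test rejects less often than its nominal 15%. The design takes the trouble to stratify and the analysis discards the gain.

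The imbalance clause does not repair this. It is triggered by imbalance, and stratification is there to prevent imbalance on this factor.

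The clause is also a gap in its own right. Adjustment is left optional, so the final primary model is not fixed before the data are seen. The trial is open-label and the principal investigator is not blinded (Justification, Objective, & Research Design, item 2). Aim 2 is meant to supply the effect size for a confirmatory trial, so both its interval and the identity of the primary model matter.

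**Working it through.** **Inputs from the documents:** 54 randomised 2:1 in random blocks of 3 and 6 within chemotherapy strata; 46 evaluable (31 vs 15); two-sided alpha 0.15; standardised effect 0.50; SD 17.04 ("we had a standard deviation of cumulative symptom burden from a similar symptom inventory of 17.04"), so a target of 8.52 points; pre-post correlation r given as 0.65 in one place and 0.5 in another (Sample Size and Data Analysis, item 1). Both are used.

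**Assumptions not in the documents:** R², the share of Week 6 variance left after Week 0 severity that chemotherapy explains, set at 0, 2, 5, 10 and 20%; a 33/21 split on chemotherapy; dropout at random.

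**1. The plan's own figure.** The standard error in SD units is √(1 − r²) × √(1/31 + 1/15).
- r = 0.65: 0.760 × 0.3145 = 0.239. Power = Φ(0.50/0.239 − 1.44) = 74.3%, or 73.5% with the t distribution.
- r = 0.50: 65.4%, or 64.6% with t.

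The stated 80% is not reproduced. That is a separate matter, and nothing below depends on it.

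**2. What each R² means in points.** The residual SD at r = 0.65 is 17.04 × 0.760 = 12.95. With a split p = 33/54, the baseline-adjusted chemotherapy difference is 12.95 × √(R²/[p(1 − p)]) = 12.95 × √R² / 0.4875.
- R² of 2, 5, 10 and 20% gives 3.8, 5.9, 8.4 and 11.9 points.

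The last two are strong assumptions beside a treatment target of 8.52.

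**3. Simulation** (20,000 trials per cell; Monte Carlo error about 0.25 points for type I error and 0.3 for power). Each cell is stratum omitted / included.

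| r | R² | Type I error, % | Power, % | Gain, points |
|---|---|---|---|---|
| 0.65 | 0 | 14.7 / 14.7 | 73.5 / 73.5 | 0.0 |
| 0.65 | 2% | 14.5 / 14.6 | 72.7 / 73.1 | 0.4 |
| 0.65 | 5% | 14.1 / 14.9 | 73.4 / 74.6 | 1.2 |
| 0.65 | 10% | 13.6 / 15.4 | 74.1 / 76.6 | 2.5 |
| 0.65 | 20% | 11.8 / 15.3 | 74.4 / 80.1 | 5.7 |
| 0.50 | 0 | 15.3 / 15.3 | 64.2 / 64.1 | −0.1 |
| 0.50 | 2% | 14.4 / 14.7 | 64.5 / 65.0 | 0.5 |
| 0.50 | 5% | 13.9 / 14.9 | 64.2 / 65.5 | 1.3 |
| 0.50 | 10% | 13.7 / 15.4 | 65.0 / 67.9 | 2.9 |
| 0.50 | 20% | 11.5 / 15.0 | 65.0 / 71.6 | 6.6 |

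Mean bias was under 0.06 points in every cell. Other splits at r = 0.65 (12,000 trials) gave gains at R² of 5, 10 and 20% of 1.4, 2.6 and 5.9 points (27/27) and 1.3, 2.6 and 5.6 points (43/11). A separately written simulation (8,000 trials, chemotherapy in 50% or 70%) gave gains of 1.2–1.3, 2.3–2.6 and 5.4–5.7 points. Its type I error with the stratum omitted was 13.6–14.4, 13.1 and 11.0–11.8%.

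**4. Standard errors in points, r = 0.65.**

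| R² | Mean SE reported, omitted | True SD, omitted | Mean SE, included |
|---|---|---|---|
| 5% | 4.09 | 4.04 | 3.99 |
| 10% | 4.09 | 3.91 | 3.88 |
| 20% | 4.10 | 3.79 | 3.66 |

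The reported SE is 4.09/3.99 = 1.025, 4.09/3.88 = 1.054 and 4.10/3.66 = 1.120 times the adjusted one. As a check on step 3 at R² = 20%: 2 × [1 − Φ(1.44 × 4.10/3.79)] = 11.9%, against 11.8% simulated.

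**5. Would the imbalance clause bring chemotherapy in?** Under the planned blocks, chemotherapy differed between arms at p < 0.15 in 0.05–0.4% of simulated trials, and at p < 0.05 in under 0.03%. It almost never would.

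**6. The clause itself** (31 vs 15, r = 0.65, no treatment effect, 3 or 6 candidate covariates each with R² of 2% or 5%, imbalance threshold 0.05 or 0.15).
- Model fixed in advance: 14.6–15.2%.
- Rule followed mechanically: 12.6–14.9%.
- Smaller p-value kept: 15.8–18.1%.

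Without any imbalance trigger, and with the most favourable model kept, 1, 3, 5 or 10 optional covariates jointly explaining 10% of residual variance gave about 19, 23, 24 and 27%. That is a worst case.

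**The case against.** The strongest reply is that little of substance is lost. Aim 2 seeks a preliminary estimate, and the estimate is unbiased. Most of the wider interval is an overstated standard error rather than lost information. By the table in step 4, the unadjusted estimate is truly less precise by only 4.04/3.99, 3.91/3.88 and 3.79/3.66, that is 1.3, 0.8 and 3.6%. This is correct. But the interval and p-value that get reported use the overstated standard error, so the cost appears in the result that readers see.

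The larger R² values have no support in the documents. Eligibility places Week 0 around or soon after the end of treatment and excludes chemotherapy planned during the study, so the Week 0 score may already carry much of any chemotherapy effect. This stands, and it points to the lower rows of the table.

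The imbalance clause raises the error rate only if the better-looking model is chosen, which the plan does not propose, and the size depends on how many covariates one imagines. This also stands. The clause is a gap in pre-specification, not a demonstrated inflation.

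Finally, the absence of bias and the near-perfect balance were simulated with dropout at random. If dropout depends on both arm and chemotherapy, neither is assured. None of these points argues for leaving the stratum out.

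**Conclusion.** The point holds. Omitting the stratum is a loss of efficiency and a miscalibrated standard error, not a threat to validity, and the error is in the conservative direction. With R² of 0–5% the cost is 0 to about 1.4 power points and a true type I error of about 14–15%. At 10% it is about 2.5–3 points and 13–13.7%. At 20%, a strong assumption, it is about 5.5–6.6 points and 11–12%. The open covariate clause is a smaller, separate weakness that would inflate the error rate only under selective reporting. The change should be made because it is nearly free and precision is scarce with 31 against 15 participants. The figures rest on the assumed R², the assumed chemotherapy split (which matters little) and random dropout.

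**What to change.** In the analysis plan for Aim 2:

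1. Specify the primary ANCOVA as Week 6 severity on arm, Week 0 severity and chemotherapy (yes/no, as used for randomisation). State that chemotherapy is also a fixed covariate in the other ANCOVAs, including Week 12, and in the mixed models.
2. Replace the imbalance sentence with one saying that any further adjustment, for example for age, is a sensitivity analysis whose covariates are named before the data are analysed.

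The cost is two sentences and one degree of freedom. The variable is already collected for randomisation. If chemotherapy turns out not to be prognostic, the simulated power is 73.5% with or without it at r = 0.65, and 64.1% against 64.2% at r = 0.50.
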